6.4.6 Interim Analyses

Preliminary analyses of PKs may be done once per dose level as the data for each dose level is obtained. This will be used to inform decisions about the dose levels to be administered in studies that may begin while VRC 605 is still in progress.

7. PHARMACY PROCEDURES

The study groups and study product dosing schedule are shown in Table 3. Refer to the IB for further information about the investigational study product.

7.1 STUDY PRODUCT AND ADMINISTRATION REGIMEN

VRC-HIVMAB075-00-AB (VRC07-523LS) is supplied at a concentration of $100 \text{ mg/mL} \pm 10 \text{ mg/mL}$ in an isotonic, sterile solution; two fill volumes are available: $2.5 \pm 0.1 \text{ mL}$ in a 3 mL glass vial and $6.25 \pm 0.1 \text{ mL}$ in a 10 mL glass vial. Vials contain a clear, colorless to yellow liquid essentially free of visible particles; some opaque or translucent particles may be present. The formulation buffer is composed of 50 mM Histidine, 50 mM Sodium Chloride, 5% Sucrose, and 2.5% Sorbitol at pH 6.8. Vials are intended for single-use only and thus do not contain a preservative.

In this trial, dose is limited or established based on subject weight. In calculating the dose to administer and number of vials to thaw, it should be assumed that the concentration is 100 mg/mL and that a volume of at least 6 mL can be withdrawn from a vial. Preparation of VRC07-523LS for IV administration will require a 100 mL bag of 0.9% sodium chloride, USP (normal saline). Note that the normal saline bags referred to as “100 mL bags” in the IV administration instructions will typically have 103 mL volume before any VRC07-523LS is added and this is acceptable in the context of the instructions below. Preparation of VRC07-523LS for SC administration will not require any diluent.

There are 7 different schedules in the study described in Section 4.

7.2 VRC HIVMAB075-00-AB (VRC07-523LS) VIALED PRODUCT

The VRC07-523LS product label designates the long-term storage temperature as -35°C to -15°C. Clinical site storage in a qualified, continuously monitored, temperature-controlled freezer with temperature excursions -45°C to -10°C is acceptable.

Following thaw, VRC07-523LS vials may be stored for up to 24 hours at controlled room temperature (maximum 27°C) and/or up to 2 weeks at 2°C to 8°C. Product may not be stored in direct sunlight. If stored at 2-8°C, vials must be equilibrated at controlled room temperature (maximum 27°C) for a minimum of 30 minutes and may be held at room temperature for up to 8 hours prior to product preparation.

7.3 TEMPERATURE EXCURSIONS

The site pharmacist must promptly report any storage temperature excursions outside of the normal allowance for the storage device to the IND Sponsor (Appendix II). The affected product must be quarantined in a separate area. The IND Sponsor will notify the site pharmacist if continued clinical use of the product is acceptable.

7.4 PREPARATION OF STUDY PRODUCT FOR ADMINISTRATION

This section describes how the site pharmacist will prepare the study product for administration and how the clinician will administer the product. Clinician instructions on how to select an administration site are in Section 4.2.3.

VRC07-523LS is a highly concentrated protein solution and may develop white, opaque to translucent particles after thawing. When particles are observed, they may disappear after a few hours at room temperature or storage at 2°C to 8°C.

The following instructions apply to thawing VRC07-523LS:

1. Thaw vial(s) for a minimum of 1 hour at controlled room temperature (maximum 27°C) after removing from the freezer.
2. Keep the material at room temperature during the entire preparation period until use, up to the maximum storage times described in Section 7.2.
3. Prior to preparation for administration, vials should be swirled for 30 seconds with sufficient force to resuspend any visible particles, yet avoiding foaming. **DO NOT SHAKE THE VIALS.** If particles are observed, return the vials to 2°C to 8°C storage. If the particles redissolve within the maximum storage times described in Section 7.2, the vials may be used for product preparation. **If particles continue to be observed, do not use the vialed product for SC or IV administration.** Refrigerated product must be equilibrated at controlled room temperature (maximum 27°C) for a minimum of 30 minutes before preparation and must be used within 8 hours of any subsequent return to room temperature.
4. If the thawed material is not administered within 24 hours of thaw, follow the storage information provided in Section 7.2.

Preparation is to be done using aseptic technique, in a laminar flow biosafety cabinet. Assure that only the required vials are present in the preparation unit during dilution, and medication labels are strictly segregated to avoid mix-ups. More information on product preparation can be found in the IB.

7.4.1 VRC-HIVMAB075-00-AB: Preparation for Administration Intravenously

For each IV infusion order, the subject's weight and dose level or randomization code will be included in the pharmacy order. To prepare an IV infusion, the pharmacist will calculate the total milligrams needed, retrieve the minimum number of thawed, particle free vials needed to prepare the full dose and add the calculated total mg needed to a 100 mL bag of normal saline using good pharmacy practices to maintain sterility. Prior to preparation for administration, vials should be gently swirled for 30 seconds avoiding foaming. DO NOT SHAKE THE VIAL. Typically, 50 to 100 mL of additional volume may be added to a 100 mL bag of normal saline. Each pharmacist should test the capacity of the brand of saline bags that will be used at the site to confirm the capacity to add additional volume.

An in-line filter infusion set must be used for IV product administrations. In-line filters must comply with the following specifications: 1.2 micron PES (polyethersulfone) filter membrane, DEHP-free, latex-free (equivalent to Braun #473994 filter extension set). When the in-line filter is added to the tubing, prime the administration set. Flush the administration set with about 30 mL or appropriate volume of normal saline at the end of product administration

The study product solution will typically be administered IV over about 15 to 30 minutes or more as needed using a volumetric pump. The total time needed to administer the dose may be longer based on factors such as subject tolerance. The rate of infusion may range from 10-20 mg/kg/hr with the lowest dose group to 80-160 mg/kg/hr with the highest dose group. The mL/hr infusion rate may vary based on the total volume needed to administer a full dose.

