4. STUDY DESIGN

This is an open-label, dose-escalation study to examine the safety, tolerability, dose, and PK of VRC07-523LS in healthy adults. The hypothesis is that VRC07-523LS administration will be safe by the IV and SC routes. The secondary hypothesis is that VRC07-523LS will be detectable in human sera with a definable half-life. The study schema is shown in Table 3.

Table 3: VRC 605 Study Schema

Group	Subjects	Administration Schedule		
		Day 0	Week 12	Week 24
1	3	1 mg/kg IV		
2	3	5 mg/kg IV		
3	3	5 mg/kg SC		
4	3	20 mg/kg IV		
5	3	40 mg/kg IV		
6	5	5 mg/kg SC	5 mg/kg SC	5 mg/kg SC
7	5	20 mg/kg IV	20 mg/kg IV	20 mg/kg IV
Total*	25	*The expected enrollment is 25 subjects. Enrollment up to a total of 40 subjects is permitted if additional subjects are necessary for safety or PK evaluations (Section 4.3).		

Enrollment will begin in the 1 mg/kg IV dose group (Group 1). Enrollments into the subsequent dose and route groups may proceed after dose and route escalation reviews (Section 4.3). Subjects in Groups 1 through 5 will be expected to be available for follow-up visits during 24 weeks of study participation; subjects in Groups 6 and 7 will be expected to be available for follow-up visits during 48 weeks of study participation

For each new dose level (1 mg/kg, 5 mg/kg, 20 mg/kg and 40 mg/kg) and for the initial SC group, following the first product administration, the study team will wait at least 2 days before administering VRC07-523LS to a second subject within the same group. Safety review decisions and the status of the enrollment process will be transparent to the Protocol Safety Review Team (PSRT) throughout the trial and discussed during the weekly safety review.

Safety laboratory samples will be collected throughout the study as per the Schedule of Evaluations. Subjects will keep a daily diary of solicited systemic symptoms for 3 days after each product administration. PK samples will be collected at specified intervals through 24 weeks after a subject's last product administration.

When the subject agrees, optional oral samples will be collected at specified intervals for the purpose of detecting if measurable levels of VRC07-523LS can be found in oral mucosa.

The study will be conducted by the VRC Clinical Trials Program at the NIH Clinical Center (NIH CC).

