4.2.3 Administration of VRC07-523LS

All study product administrations will be completed according to the assigned group. For women of childbearing potential, product administration may not proceed unless a negative pregnancy test has been obtained within the previous 24 hours. Prior to each product administration, temperature, blood pressure, heart rate (pulse) and weight will be collected and a targeted physical examination (based on signs, reported symptoms or interim medical history) may be conducted. In all study groups, the subject will be observed for at least 4 hours following each product administration.

If a subject is assigned to an IV administration group, the IV access will be placed in an arm vein in an aseptic manner. A different site may be used for collection of PK blood samples; however, the same site may be used after flushing the line if another site is not available. VRC07-523LS will be administered with approximately 100 mL normal saline IV over about 30 minutes or longer. If the subject experiences side effects during the infusion, the rate of infusion may be slowed or stopped to alleviate the symptoms.

If a subject is assigned to a SC administration group, the SC administration site(s) to be used will be discussed with the subject and must be assessed as acceptable by the clinician and the subject. The preferred SC administration site is the abdomen, but the upper arm or thigh may be used. Given the weight criterion in this study, the maximum volume needed to administer a 5 mg/kg SC dose is not expected to exceed 5.75 mL. The SC dose will be administered by standard needle and syringe SC injection methods with about 2.5 mL per injection site. Up to 4 SC injection sites may be used if deemed necessary by the clinician. SC administration sites should be at least 2 inches apart.

Procedures for VRC07-523LS preparation and administration are described in Section 7.

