There are several FDA-licensed MAbs for which reactions related to the rate of IV infusion have been described. Some symptoms may be treated by slowing or stopping the infusion. Supportive treatment may also be indicated for some signs and symptoms.

Participation in this study may limit a subject's eligibility for future MAb studies.

Risks of Blood Drawing: Blood drawing may cause pain and bruising and, infrequently, may cause a feeling of lightheadedness or fainting. Rarely, it may cause infection at the site where blood is taken. In this study, an IV line that can be used for blood collection may be placed and left in place for several hours on the days when there are frequent PK blood draws. Problems from use of an IV for blood drawing are generally mild and may include pain, bruising, minor swelling or bleeding at the IV site and rarely, infection, vein irritation (called phlebitis), or blood clot.

Risks of Oral Mucosa Sample Collection: Collection of samples by swabs and wicks rubbed over the mucosal surfaces may cause momentary discomfort and, in some cases, minor bleeding.

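### Section 7.4.1 gives the lowest IV dose group an infusion rate five times too high, and its infusion time conflicts with Section 4.2.3 below 30 minutes

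*Combined protocol and SAP*

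**What the plan says.** Section 7.4.1 (preparation for IV administration) says the solution "will typically be administered IV over about 15 to 30 minutes or more as needed using a volumetric pump". It then translates this into rates: "The rate of infusion may range from 10-20 mg/kg/hr with the lowest dose group to 80-160 mg/kg/hr with the highest dose group".

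Section 4.2.3 (administration) says the product "will be administered with approximately 100 mL normal saline IV over about 30 minutes or longer". It adds that, if side effects occur during the infusion, "the rate of infusion may be slowed or stopped to alleviate the symptoms".

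The two sections are linked. Section 4.2.3 ends with "Procedures for VRC07-523LS preparation and administration are described in Section 7", and Section 7.4 announces that it covers "how the clinician will administer the product".

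Table 3 in Section 4 sets the IV dose levels: 1 mg/kg (Group 1), 5 mg/kg (Group 2), 20 mg/kg (Groups 4 and 7) and 40 mg/kg (Group 5). The lowest IV dose group is therefore 1 mg/kg and the highest 40 mg/kg.

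**The concern.** There are two problems. First, the rate quoted for the lowest dose group does not follow from the lowest dose and the infusion time in the same paragraph. Second, Section 7.4.1 accepts infusions from about 15 minutes, whereas Section 4.2.3 starts at about 30. Both sections present themselves as administration instructions, and no text gives one precedence.

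These are operating instructions for a product not given to humans before this study, and the protocol itself treats rate as relevant to safety. Section 7.5 notes: "There are several FDA-licensed MAbs for which reactions related to the rate of IV infusion have been described". There is also a compliance consequence. Section 5.4.2 counts any departure from IRB-approved procedures as a protocol deviation, so a 20-minute infusion conforms to Section 7.4.1 but arguably not to Section 4.2.3. Staff and monitors could classify it differently.

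**Working it through.** **Inputs.** IV doses of 1, 5, 20 and 40 mg/kg (Section 4, Table 3). Infusion time of about 15 to 30 minutes or more (Section 7.4.1), or about 30 minutes or longer (Section 4.2.3). Stated rates of 10-20 mg/kg/hr for the lowest group and 80-160 mg/kg/hr for the highest (Section 7.4.1).

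**Formula.** Rate (mg/kg/hr) = dose (mg/kg) / time (hr), with 30 minutes = 0.5 hr and 15 minutes = 0.25 hr. Body weight does not enter, because both dose and rate are per kg.

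**Reproducing the plan's figure for the highest group.** 40 / 0.5 = 80 and 40 / 0.25 = 160. This matches 80-160 exactly, so the sentence was evidently built from 15 to 30 minutes.

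**All dose levels by the same method:**

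| IV dose (mg/kg) | Rate over 30 min | Rate over 15 min | Stated in Section 7.4.1 |
|---|---|---|---|
| 1 | 1 / 0.5 = 2 | 1 / 0.25 = 4 | 10-20 (lowest group) |
| 5 | 5 / 0.5 = 10 | 5 / 0.25 = 20 | not stated |
| 20 | 20 / 0.5 = 40 | 20 / 0.25 = 80 | not stated |
| 40 | 40 / 0.5 = 80 | 40 / 0.25 = 160 | 80-160 (highest group) |

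The lowest-group figure is off by 10 / 2 = 20 / 4 = 5, and 10-20 coincides with the 5 mg/kg row.

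**Reverse check.** At 10 mg/kg/hr, 1 mg/kg takes 1 / 10 = 0.10 hr = 6 minutes. At 20 mg/kg/hr it takes 1 / 20 = 0.05 hr = 3 minutes. Both fall below either section's infusion time. An infusion longer than 30 minutes only lowers the rate below 2 mg/kg/hr, so the open-ended wording does not rescue the figure.

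**The two infusion times.** The shortest time under Section 4.2.3 gives top rates of about 2, 10, 40 and 80 mg/kg/hr for 1, 5, 20 and 40 mg/kg. The shortest time under Section 7.4.1 gives 4, 20, 80 and 160. The ratio is 2 throughout (for example 80 / 40 and 160 / 80). Under Section 4.2.3, rates above about 80 and up to 160 mg/kg/hr for the highest group would not arise.

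**The case against.** The strongest reply grants the arithmetic and disputes the weight.

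- **Group 1 is largely past.** Under Section 4.3, Group 2 could open only after at least 3 subjects had received 1 mg/kg and completed 2 weeks of safety follow-up. Section 1.3.3 reports the final safety review on August 9, 2017. Group 1 is single-dose, so the wrong rate matters in practice only if subjects are added there. This stands.
- **The figure is unlikely to be followed.** It is worded as a description, and the pharmacist works from weight and dose level. With the 103 mL bag of Section 7.1 and ignoring the drug volume, 3 to 6 minutes would need 103 / 0.05 = 2,060 to 103 / 0.10 = 1,030 mL/hr, against 206 to 412 mL/hr over 30 to 15 minutes. A clinician would probably notice. This also stands.
- **The time conflict is narrow.** Both phrases are approximate, and 30 minutes or more complies with both. This is true, but an allowance for approximation does not stretch 30 minutes to 15. The gap still affects the 20 and 40 mg/kg infusions, including three per subject in Group 7.
- **No hazard is shown.** Section 7.5 speaks of licensed antibodies and expects a low risk of immune reactions with this one. Section 1.3.3 reports no SAEs, no related AEs and no safety pauses up to July 17, 2017. Infusions can be slowed or stopped, subjects are observed for at least 4 hours, and exact start and end times are recorded (Appendix III). No text says that 15 minutes is unsafe.

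These points limit urgency. They do not make the stated rate correct or settle which time applies.

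**Conclusion.** The concern holds on both counts. The lowest-group rate is wrong by a factor of 5 (10-20 stated, 2-4 mg/kg/hr correct for 15 to 30 minutes). The two sections also differ by a factor of 2 in the shortest infusion time and hence in the top rate; this conflict is confined to infusions of 15 to under 30 minutes.

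The first result assumes only that the lowest dose group means the 1 mg/kg group, as Table 3 shows. The second takes each section's approximate time at face value.

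The time conflict matters more in practice, because it applies to the 20 and 40 mg/kg doses. The practical effect is modest: total dose, sample size, safety tables and PK methods do not change. It should be corrected because these are working instructions for a first-in-human antibody, but it is not a reason to hold up the study.

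**What to change.** State one minimum infusion time in both sections and give the rates by dose level. The sponsor's clinical and pharmacy team must decide which time governs.

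- **If 15 to 30 minutes is kept:** change the time in Section 4.2.3 to match, and give 2-4, 10-20, 40-80 and 80-160 mg/kg/hr for 1, 5, 20 and 40 mg/kg in Section 7.4.1. This changes one phrase in Section 4.2.3 and the rate sentence in Section 7.4.1.
- **If 30 minutes is the minimum:** leave Section 4.2.3 alone, and change Section 7.4.1 to that time with rates of at most about 2, 10, 40 and 80 mg/kg/hr. This changes two sentences in Section 7.4.1.

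Under Section 8.1 either is a protocol amendment, needing prior IND Sponsor approval, agreement of the PI and the Medical Officer, and IRB submission. It can go in the next amendment. No analysis or sample-size text needs to change.

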7.4.2 VRC-HIVMAB075-00-AB: Preparation for Administration Subcutaneously

For each SC administration order, the subject's weight and dose level or randomization code will be included in the pharmacy order. To prepare a SC administration dose, the pharmacist will calculate the total mg needed and retrieve the minimum number of thawed, particle free vials needed to prepare the full dose. Prior to preparation for administration, vials should be gently swirled for 30 seconds avoiding foaming. DO NOT SHAKE THE VIALS. If particles are observed, follow instructions in Section 7.4.

The needed volume of VRC07-523LS must be withdrawn from the vial into 1 to 4 syringes (BD Luer-Lok mL syringe; REF # 309657) using a 5 micron filter needle (BD Blunt Fill Needle – Filter, 18G 1 ½ inch; REF# 305211). A new filter needle must be used for each syringe. The filter needle must be discarded prior to dispensing and replaced with a needle suitable for SC injection at the time of administration.

The product may be administered by direct SC injection with needle and syringe or using a SC infusion pump at a rate of 15 mL/hr. The clinician will use proper SC technique to ensure administration into SC fatty layer and a slow push to minimize discomfort or the excessive distention of overlying skin. The length of time to complete the infusion will vary depending on the subject's weight and tolerance of the infusion rate.

7.4.3 VRC -HIVMAB075-00-AB (VRC07-523LS) Prepared Product (IV Bag and Syringe)

After product preparation in IV bags, the prepared VRC07-523LS may be stored at 2oC to 8oC up to 24 hours or at room temperature (maximum 30oC) for a maximum of 8 hours total including the infusion time. Product may not be stored in direct sunlight. If stored at 2oC to 8oC, prepared product must be equilibrated at room temperature (maximum 30oC) for a minimum of 30 minutes prior to product administration.

After preparation in syringes for SC administration, the prepared VRC07-523LS may be stored at 2oC to 8oC up to 24 hours or at room temperature (maximum 30oC) up to 4 hours. Product may not be stored in direct sunlight.

Each institution will need to follow their policies for expiration dates if shorter than the timeframes specified here or in the IB.

7.5 RISKS

Risks of Administration of MAbs: Administration of MAbs may have a risk of immune reactions such as acute anaphylaxis, serum sickness and the generation of antibodies. However, these reactions are rare and more often associated with MAbs targeted to human proteins or with the use of murine MAbs that would have a risk of human anti-mouse antibodies [20]. In this regard, because VRC07-523LS is targeted to a viral antigen and is a human MAb, it is expected to have a low risk of such side effects.

Typically, the side effects of MAbs are mild and may include reactions at injection site (pain, redness, bruising swelling), fever, chills, rigors, nausea, vomiting, pain, headache, dizziness, shortness of breath, bronchospasm, hypotension, hypertension, pruritus, rash, urticaria, angioedema, diarrhea, tachycardia or chest pain. Clinical use of MAbs that are targeted to cytokines or antigens associated with human cells may be associated with an increased risk of infections [20]; however, this is not expected to be a risk for a MAb targeted to a viral antigen.

It is known from published experience with human MAbs directed against the cell surface targets on lymphocytes that infusion of a MAb may be associated with cytokine release, causing a reaction known as “cytokine release syndrome” (CRS) [21]. Most infusion-related events occur within the first 24 hours after beginning administration. Severe reactions, such as anaphylaxis, angioedema, bronchospasm, hypotension and hypoxia, are infrequent and more often associated with MAbs targeted to human proteins or with non-human MAb, such as a murine MAb [20]. CRS reactions most commonly occur within the first few hours of beginning infusion and with the first MAb infusion received. This is because the cytokine release is associated with lysis of the cells targeted by the MAb and the burden of target cells is greatest at the time of the first MAb treatment. With licensed therapeutic MAbs, CRS is managed by temporarily stopping the infusion, administering histamine blockers and restarting the infusion at a slower rate [22].

Delayed allergic reactions to a MAb may include a serum sickness type of reaction, which is characterized by urticaria, fever, lymph node enlargement, and joint pains. Symptoms may not appear until several days after the exposure to the Mab. This type of reaction is noted to be more common with chimeric types of MAb [20].

There are several FDA-licensed MAbs for which reactions related to the rate of IV infusion have been described. Some symptoms may be treated by slowing or stopping the infusion. Supportive treatment may also be indicated for some signs and symptoms.

Participation in this study may limit a subject's eligibility for future MAb studies.

Risks of Blood Drawing: Blood drawing may cause pain and bruising and, infrequently, may cause a feeling of lightheadedness or fainting. Rarely, it may cause infection at the site where blood is taken. In this study, an IV line that can be used for blood collection may be placed and left in place for several hours on the days when there are frequent PK blood draws. Problems from use of an IV for blood drawing are generally mild and may include pain, bruising, minor swelling or bleeding at the IV site and rarely, infection, vein irritation (called phlebitis), or blood clot.

Risks of Oral Mucosa Sample Collection: Collection of samples by swabs and wicks rubbed over the mucosal surfaces may cause momentary discomfort and, in some cases, minor bleeding.

